Galveston Orientation and Amnesia Test (GOAT)⁷⁷: A measure of orientation to place, time, and personal information used to assess post-traumatic amnesia.

Cognitive Therapy Awareness Scale (CTAS)⁷⁸: A 40-item, self-report, true-false measure of knowledge of basic CBT skills. The CTAS is a simple, brief measure that has been used in a number of studies.^{78,79,80,81} A score of 20 is suggested to be the average score obtained by individuals with no awareness of cognitive therapy.⁸²

Substance Use Questionnaire: A 15-item, self-report questionnaire that assesses if the patient used psychoactive substances in the last 30 days.

*The Alcohol Use Disorders Identification Test*: A 3-item, clinician-rated measure of alcohol consumption that can help identify individuals who are hazardous drinkers or have active alcohol use disorders.⁸³

PROMIS Pain Intensity: Measures how much a person hurts.⁸⁴

PROMIS Pain Interference: Measures consequences of pain on relevant aspects of one's life. This includes the extent to which pain hinders engagement with social, cognitive, emotional, physical, and recreational activities.⁸⁵

Depression Measures:

*Inventory of Depressive Symptomology (IDS-C30)*⁸⁶ (*primary outcome*): 30-item clinician rated scale that assesses severity of depression according to the nine DSM-IV⁵¹ symptom domains.

*Quick Inventory of Depressive Symptomatology, Clinician-Rated (QIDS-C)*⁸⁷: 16-item clinicianrated scale that assesses severity of depression according to the nine DSM-IV⁵¹ symptom domains.

Columbia-Suicide Severity Rating Scale (C-SSRS)⁸⁸: Clinician assessment of recent through lifetime suicidal ideation and behavior (i.e., attempts, interrupted and aborted attempts, preparatory behavior, and nonsuicidal self-injury).

Beck Depression Inventory II (BDI-II)⁸⁹: A 21-item self-rated questionnaire that assesses severity of depression.

Hospital Anxiety and Depression Scale (HADS)⁹⁰: A 14-item self-rated questionnaire that assesses severity of anxiety and depression.

PROMIS Bank v1.0: Depression: A 28 item, self-rated, Computerized Adaptive Test that assesses severity of depression. The first item is fixed for all participants, but participants' response will determine which item is selected next by the program; this is repeated for all subsequent items.

*Modified Beck Hopelessness Scale*¹³⁵: A self-report measure of negative expectations for the future that has been modified from the 20-item BHS ¹³⁶. The 10-item modified BHS uses a 5-point Likert scale, ranging from 0 (not at all) to 4 (very much), with total scores ranging from 0 to 40.

Neurological Measures:

Information about TBI diagnosis and severity will be obtained via interview and review of medical records (i.e., duration of unconsciousness, Glasgow Coma Scale (GCS)⁹¹ score, duration of posttraumatic amnesia (PTA), neuroimaging results, and inpatient and/or outpatient rehabilitation services). A Release of Information will be obtained at the screening visit in order to access the subject's medical records.

Neuropsychological Measures:

Rivermead Postconcussion Symptom Questionnaire (RPQ)⁹²: A self-report questionnaire that assesses presence and severity of somatic, cognitive, and emotional symptoms after TBI.

Wechsler Adult Intelligence Scale IV (WAIS-IV): Similarities and Digit Span subtests⁹³: The WAIS-IV is a standardized neuropsychological test battery designed to assess cognitive ability

and intelligence. The selected subtests assess verbal comprehension, working memory, and processing speed.

*Test of Premorbid Functioning (TOPF)*⁹⁴: A standardized neuropsychological test that estimates an individual's premorbid cognitive and memory functioning.

Wechsler Memory Scale IV (WMS-IV), Logical Memory subtest⁹⁵: A subtest of the WMS-IV designed to measure immediate, delayed, and auditory aspects of memory.

CNS Vital Signs: Brief, computerized, remotely administered neurocognitive test battery comprised of seven "core" subtests and three "optional" subtests measuring memory, reaction time, processing speed, executive functioning, attention, cognitive flexibility, social perception and aspects of cognition. The measures have been normed, and validity and reliability has been demonstrated in peer-reviewed publications since 2006⁹⁶.

Neuro-QOL Item Bank v2.0 Cognition Function Short Form⁹⁷: An 8-item, self-rated questionnaire assessing cognitive function.

Measures of Global Outcome:

*Glasgow Outcome Scale (GOS-E)*⁹⁸: A clinician-administered tool that assesses global functioning after brain injury using a structured interview and assigns an individual to one of eight functional categories, ranging from 1 (dead) to 8 (upper good recovery).

Measures of Social Functioning:

Neuro-QOL Item Bank v1.0 – Ability to Participate in Social Roles and Activities Short Form: An 8-item scale that assesses perceived ability to perform one's usual social roles and activities.⁹⁹

Neuro-QOL Item Bank v1.1 – Satisfaction with Social Roles and Activities Short Form: An 8item scale that assesses satisfaction with performing one's usual social roles and activities.¹⁰⁰

Measures of Emotion Regulation:

NIH Toolbox Anger-Affect Fixed Form: A 5-item self-rated questionnaire assessing the patients' experience of anger.¹⁰⁰

Neuro-QOL Item Bank v1.0 Emotional and Behavioral Dyscontrol¹⁰¹: An 8-item self-rated questionnaire assessing the patients' experience of emotional and behavioral dyscontrol.

Automatic Thoughts Questionnaire-Revised (ATQ-R)¹⁰²: A 40-item self-rated questionnaire that assesses the frequency with which an individual endorses positive and negative self-statements.

Measures of Coping and Awareness:

Coping Attitudes Scale (CAS)¹⁰³: A 23-item, self-report measure of positive attitudes, reflective of patients recovered from depression.¹⁰⁴

Awareness Questionnaire $(AQ)^{105}$ : A 17-item measure of impaired self-awareness with patient and family member forms.

NIH Toolbox Item Bank v2.0 Meaning and Purpose¹⁰¹: An 8-item self-rated questionnaire assessing the patients' feelings of meaning and purpose.

Measure of Activity: Each participant will be provided with an activity tracker while receiving the intervention (e.g. Fitbit Charge 3TM, Fitbit Charge 4TM, or a pedometer-like device) which will measure number of steps walked as an index of behavioral activation. Devices will be wireless-enabled and will sync to a computer, allowing for real time, quality controlled access to data. Patients will be provided with the device at the first psychotherapy visit (week 1). Behavioral

treatment adherence data from the activity trackers will be downloaded weekly and used to inform treatment. Specific information about the devices will be submitted to the IRB once it is obtained.

Acceptability and Satisfaction:

Satisfaction with Therapy and Therapist Scale – Revised (STTS-R)¹⁰⁶: A 12-item self-rated questionnaire assessing the satisfaction with the therapy and therapist.

Working Alliance Inventory (WAI)¹⁰⁷: A clinician-rated and a self-rated 12-item questionnaire assessing the alliance between the clinician and patient.

Post Treatment Visit Assessment: A brief survey assessing the perceived helpfulness of the subject matter discussed at each treatment visit.

End of Treatment Assessment: A brief survey assessing the feasibility and perceived helpfulness of the intervention.

Other:

Epidemic – Pandemic Impacts Inventory (EPII)¹⁰⁸: a newly developed measure designed to learn about the impact of the coronavirus disease pandemic and future epidemics and pandemics on various domains of personal and family life.

All data will be entered directly into REDCap by the study clinicians and subjects. Completion of web-based, self-report measures via computer or tablet is likely to be more appealing to the study population who may experience physical injuries that impact writing abilities. Further, use of REDCap will likely minimize missing self-report study data and allow for immediate follow up on missing items, which is likely to be relevant for individuals who have sustained TBIs and frequently experience problems with attention and concentration. In the event that circumstances inhibit the ability to directly enter the data electronically (via computer or tablet), paper copies will be provided for clinician-rated or self-report administration. These paper copies will be directly downloaded from REDCap to ensure that the measures look identical to the electronic copies.

Table 1 below outlines the schedule of assessments for each phase of the study

Assessment	Screen	Wk 1	Wk 2	Wk 3	Wk 4	Wk 5	Wk 6	Wk 7	Wk 8	Wk 9	Wk 10	Wk 11	Wk 12 / Last Visit	3mo F/u
Informed Consent;	Х													
UBACC	37		-											
Inclusion/Exclusion Criteria	X													
Demographics/ Contact Information	Х													
Clinician Administered Psychiatric History Form	X													
OSU TBI Form	Х													
Release of Information	Х													
GOAT	Х													
MINI	Х													
C-SSRS	Х												Х	Х
AUDIT-C	Х													
Substance Use Questionnaire	Х													
Concomitant Treatment Log	Х		Х		Х		Х		Х		Х		Х	Х
Adverse Events			Х		Х		Х		Х		Х		Х	Х
CTAS	Х												Х	Х
IDS-C	Х												Х	Х
GOS-E	Х												Х	Х
QIDS-C			Х		Х		Х		Х		Х			
PROMIS Depression	Х		Х		Х		Х		Х		Х		Х	Х
BDI-II	Х	Х	Х	Х	Х	Х	Х	Х	Х	Х	Х	Х	Х	Х
HADS	Х												Х	Х
RPQ	Х						Х						Х	Х
Neuropsych Battery (see separate table for individual tests)	Х												Х	
Neuro-QOL Cognition Function – SF	Х												Х	Х

Table 1: Schedule of Assessments for Active CBT Patients

Anger-Affect Fixed	Х						Х						X	Х
Form														
Neuro-QOL Ability to	Х						Х						Х	Х
Participate in Social														
Roles and Activities-SF														
Neuro-QOL Satisfaction	Х												Х	Х
with Social Roles and														
Activities-SF														
Neuro-QOL Emotional	Х												Х	Х
and Behavioral														
Dyscontrol-SF														
Coping Attitudes Scale	Х						Х						Х	Х
Awareness	Х												Х	
Questionnaire (patient)														
NIH Toolbox Meaning	Х						Х						Х	Х
and Purpose														
ATQ-R	Х						Х						Х	Х
Activity Tracker (data			Х	Х	Х	Х	Х	Х	Х	Х	Х	Х	Х	
syncs wirelessly)														
WAI-SF							Х						Х	
							(patient							
							version only)							
PROMIS Pain Intensity	X						X						X	X
PROMIS Pain	Х						Х						Х	Х
Interference														
Beck Hopelessness Scale	Х												Х	Х
STTS-R and interview													Х	
Post treatment		Х	Х	Х	Х	Х	Х	Х	Х	Х	Х	Х		
assessment (participant)														
Homework Compliance			Х	Х	Х	Х	Х	Х	Х	Х	Х	Х	Х	
(therapist)														
End of Treatment													Х	
Feedback														
COVID-19	Х												Х	Х
Supplemental Survey														
Approximate Time	240	< 10	30	< 10	30	< 10	45	< 10	30	< 10	30 min	< 10	180 min	60 min
Estimate	min	min	min	min	min	min	min	min	min	min		min		

Table 2. Schedule of Assessments for Waitlist Patients (note: after WL week 12 patients continue with Active CBT Assessments for 12 weeks)

Assessment	Screen	WL Wk 2	WL Wk 4	WLWk 6	WL Wk 8	WL Wk 10	WL Wk 12 / Last Visit
Informed Consent; UBACC	Х						
Inclusion/Exclusion Criteria	Х						
Demographics/ Contact Information	Х						
Clinician Administered Psychiatric History Form	X						
OSU TBI Form	Х						
Release of Information	Х						
GOAT	Х						
MINI	Х						
C-SSRS	Х						
AUDIT-C	Х						Х
Substance Use Questionnaire	X						
Concomitant Treatment Log	Х	X	X	X	Х	X	Х
Adverse Events		X	Х	X	X	X	Х
CTAS	Х						Х
IDS-C	Х						Х
GOS-E	Х						Х
QIDS-C		Х	Х	X	Х	Х	
PROMIS Depression	Х	Х	Х	X	Х	X	Х
BDI-II	Х						Х
HADS	Х						Х
RPQ	Х						Х
Neuropsych Battery (see separate table for individual tests)	Х						X

Neuro-QOL Cognition	Х						Х
Function – SF							
Anger-Affect Fixed	Х						Х
Form							
Neuro-QOL Ability to	Х						Х
Participate in Social							
Roles and Activities-SF							
Neuro-QOL Satisfaction	Х						X
with Social Roles and Activities-SF							
Neuro-QOL Emotional	Х						Х
and Behavioral							
Dyscontrol-SF							
Coping Attitudes Scale	Х						Х
Awareness	Х						Х
Questionnaire (patient)							

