 - b. GCS 3–12 with GCS motor score =6 within 4 hours after injury AND documented intracranial abnormalities on imaging
 - c. GCS 13–15 within 4 hours after injury AND documented intracranial abnormalities on imaging
 - d. Loss of consciousness (LOC) > 30 min.
 - e. Post-traumatic amnesia (PTA) > 24 hours
- 8. Out of PTA at the time of enrollment (GOAT>75)
- Clinically significant depressive symptoms: meets criteria for Major Depressive Episode on the MINI or has a total score ≥ 23 on the Inventory of Depressive Symptomatology – Clinician rated (IDS-C)

Exclusion criteria:

- 1. Uncontrolled medical illness
- 2. Behavioral dyscontrol, defined as the presence of verbally or physically aggressive behavior in the past month, as evidenced in medical records, pre-screening interviews, or observed by any study staff
- 3. Presents with PTSD as the primary diagnosis, as determined by a clinician
- 4. Substance use disorder, moderate or severe, within the past 6 months
- 5. Has bipolar disorder, a primary psychotic disorder or current psychotic symptoms, or acute suicidality or homicidality
- 6. Currently receiving regular (≥ 2 times/mo.) psychosocial treatment for depression
- 7. Has participated in CBT for depression within the past 6 months
- 8. Individuals with history of dementia or severe cognitive impairment that is not related to TBI (e.g., cognitive impairment requiring assistance with basic activities of daily living, such as getting ready in the morning)

Recruitment: Subjects will be recruited through a number of sources. Spaulding Rehabilitation Hospital (SRH) will be the main recruitment site.

Outpatient Clinics

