of a meeting with a clinician for a structured diagnostic interview and assessment of depressive severity and neuropsychiatric symptoms, the completion of self-report questionnaires, and neuropsychological testing. This visit may be split into two parts, with the neuropsychological assessment occurring during the second part, in order to accommodate subjects' potential limitations due to fatigue.

In the first phase of recruitment, we will enroll 10 subjects in order to pilot test the newly developed manual in a nonrandomized, open trial. Based on objective and qualitative feedback from participants, the CBT-TBI manual, which includes materials such as CBT homework and study diaries, will then be revised.

Once the CBT-TBI manual has been revised, we will enroll up to 60 subjects in the second phase of recruitment with the goal of randomizing 40 participants. They will be enrolled using the same procedure as described in the open trial (N=10), but eligible participants will be randomly assigned in consecutive order to intervention or waitlist control group. Given that history of pre-injury MDD is the strongest predictor of post-TBI depression¹² and the higher incidence of MDD in women than in men,⁷³ randomization will be stratified by history of MDD and gender, so that both conditions include the same number of subjects with and without pre-injury MDD, as well as males and females. The randomization list will be provided by the biostatistician and maintained by the research staff. During the first 12 weeks, as per the schedule outlined below, participants randomly assigned to the waitlist control group will be seen only for assessments. Control arm participants will receive treatment as usual outside of our clinic and scheduled assessments in our clinic for 12 weeks. After 12 weeks, they will be offered the CBT-TBI treatment.

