Hypothesis 3a: CBT-TBI will result in a greater decrease in IDS-C scores after 12 weeks (*primary outcome*) compared to waitlist control. Response over 12 weeks defined by 50% or greater decrease on IDS-C total; remission ≤ 6 on IDS-C total. Continuous variables will be analyzed by generalized mixed effect modeling, which impute missing values based on maximum likelihood estimates of missing parameters, allowing analysis of all participants. A time-by-condition interaction will be analyzed to test the intervention's efficacy. Relevant potential covariates (e.g., caregiver presence) will also be examined. The percent of responders and remitters in each group will be computed in order to estimate an effect size for the R01. Although I will test for statistical significance, the primary aim of this pilot RCT is to estimate the intervention's effect size to conduct a larger, more adequately powered R01 study, as is outlined in NIH guidelines for developing behavioral interventions¹²⁸. Given that some prior studies utilizing CBT in patients with TBI suggest large effect sizes for reducing emotional distress and depressive symptoms,^{32,34} we expect similar findings.

Hypothesis 3b: CBT-TBI will produce an increase in coping skills, adaptive thinking, positive self-appraisal, social functioning and activity level compared to waitlist control, and these factors will mediate depressive outcomes. To evaluate the indirect effect of CBT-TBI to depression (IDS-C) through coping skills, adaptive thinking, positive self-appraisal, social functioning, and activity level, we will employ an SPSS macro (PROCESS) to test the significance of the indirect effect with a bootstrapping approach to obtain confidence intervals.¹²⁹ The constructed conditional process model proposes that CBT-TBI will lead to increased coping skills, adaptive thinking, positive self-appraisal, social functioning and activity level, and that increase in these mediators will result in reduced depression. Bootstrapping is superior to other methods for determining the significance of indirect effects, as the assumption of normality for the sampling distribution is not required and power is improved.¹³⁰

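### The stratification factors (pre-injury MDD and gender) are not prespecified in the efficacy model, so the reported effect-size interval may be wider than the design warrants

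*Protocol*

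**What the plan says.** Protocol section IV (Subject Enrollment) sets out the randomization in one sentence. The reason comes first: "Given that history of pre-injury MDD is the strongest predictor of post-TBI depression", with a parallel remark on the higher incidence in women. Then the method: "randomization will be stratified by history of MDD and gender". Then the goal: "so that both conditions include the same number of subjects with and without pre-injury MDD, as well as males and females". The second phase enrolls "with the goal of randomizing 40 participants". The allocation ratio and block size are not given; the text says only that "The randomization list will be provided by the biostatistician and maintained by the research staff".

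Protocol section VI (Hypothesis 3a) and the SAP (Hypothesis 2a) describe the same efficacy analysis: a mixed-effects model for continuous outcomes, with the time-by-condition interaction as the test. On covariates both say: "Relevant potential covariates (e.g., caregiver presence) will also be examined". Neither names pre-injury MDD, history of MDD or gender as a model term. The other relevant provision is a set of Mann-Whitney or chi-square tests for baseline balance.

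Two further points set the context. Both documents label efficacy an exploratory aim and say that the main purpose of the randomized pilot is to estimate an effect size for a larger trial. In Tables 1 and 2 of section V, IDS-C is scheduled only at screening and week 12 within the randomized comparison.

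**The concern.** Stratified randomization makes the arms more alike on the stratification factors than chance would. If those factors predict the outcome, the treatment estimate varies less from trial to trial. A model that omits them does not register this: it leaves the variance they explain in the residual and reports a standard error as if allocation had been unrestricted. The estimate stays unbiased, but the interval is too wide and the test is conservative.

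In a trial of 40 whose main efficacy product is an effect size with its uncertainty, that gives away precision the design has already paid for. It also leaves the choice of covariates open until the data are in hand.

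**Working it through.** **No figure to reproduce.** The documents give no SD, alpha, power or sample-size derivation for the efficacy comparison.

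**Inputs from the documents.** 40 randomized; two binary factors, so 2 × 2 = 4 strata; IDS-C at two time points.

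**Assumptions.** 1:1 allocation in permuted blocks of 4 within strata; two-sided alpha 0.05; SD of IDS-C change set to 1; effect 0.8 SD (the documents say only that effects may be large); prevalence 40% for each factor; the two factors together explain a share R² of the variance in change, split equally between them, with R² from 0 to 0.30.

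**Step 1: by hand.** With 20 per arm, an unadjusted model reports SE ≈ √(2/20) = 0.316 whatever R² is. Adjusting for the factors gives about 0.316 × √(1 − R²):

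- R² = 0.05: 0.308
- R² = 0.10: 0.300
- R² = 0.20: 0.283
- R² = 0.30: 0.265

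For reference, a two-sample comparison with 20 per arm and an effect of 0.8 SD has 71.6% power.

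**Step 2: simulation.** 6,000 trials per row, regressing change on arm, without and with the two factors. The SE columns are for the null case.

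| R² | Reported SE, unadjusted | True SE, unadjusted | Reported ÷ true | Reported SE, adjusted | Type I, unadj. / adj. | Power at 0.8 SD, unadj. / adj. |
|---|---|---|---|---|---|---|
| 0 | 0.314 | 0.311 | 1.01 | 0.315 | 4.7% / 4.7% | 70% / 69% |
| 0.05 | 0.314 | 0.307 | 1.02 | 0.307 | 4.3% / 4.8% | 71% / 73% |
| 0.10 | 0.316 | 0.299 | 1.06 | 0.299 | 4.0% / 4.7% | 69% / 72% |
| 0.20 | 0.315 | 0.284 | 1.11 | 0.281 | 3.2% / 5.0% | 71% / 79% |
| 0.30 | 0.316 | 0.273 | 1.16 | 0.265 | 2.3% / 5.1% | 71% / 83% |

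A separate run of 4,000 trials with prevalences 0.35 and 0.40 gave unadjusted type I error of 4.0%, 3.2% and 2.5% at R² = 0.10, 0.20 and 0.30, and power of 69% versus 73%, 70% versus 78%, and 72% versus 83%. The differences between runs are within simulation error: √(0.7 × 0.3 / 6,000) ≈ 0.6 percentage points for a power near 70%.

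As a 95% half-width at R² = 0.20, unadjusted is 2.02 × 0.315 = 0.64 SD and adjusted is 2.03 × 0.281 = 0.57 SD (t quantiles on 38 and 36 degrees of freedom).

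**Step 3: what has to go into the planned model.** Write the mean at time t (0 or 1) as a + b·t + c·arm + d·t·arm + g·S, where S holds the two factors, with a random intercept per person. Subtracting a person's screening value from the week-12 value leaves b + d·arm. The term g·S is the same at both times and cancels, so with complete data it cannot alter d, the tested coefficient. Adding h·t·S leaves b + d·arm + h·S, and the factors now act on change.

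A check on 150 simulated trials (n = 40, complete data, random intercept) agreed. Adding the factors as main effects left the interaction estimate the same to within 1e-14 and the mean SE at 0.2746; adding their interactions with time lowered the SE to 0.2645.

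**The case against.** The strongest reply is that the harm is small and in the safe direction. Omission does not bias the estimate, it lowers type I error, and the efficacy aim is exploratory. All of that stands. The size also rests on an R² that the documents do not supply. The reason given in section IV concerns the risk of depression, whereas the planned test concerns change over 12 weeks. A factor that predicts level but not change does nothing here, so R² may well be small. That stands too, and is why the range includes 0 and 5%.

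It can also be said that the open covariate list does not rule the factors out. That is right: a reader might infer that they are excluded from the model, but the documents show only that they are not prespecified. The planned balance tests do not fill the gap, because testing for imbalance is not adjustment.

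A reader might go further and infer that the list uses the wrong stratifier. The method clause says history of MDD, without the word pre-injury, and entry requires that a participant "meets criteria for Major Depressive Episode on the MINI or has a total score ≥ 23". Coded literally, such a stratum could be positive for most entrants and fail to balance pre-injury MDD. The documents do not support that inference. The reason and the goal on either side of the clause both say pre-injury, so the short form reads naturally as shorthand. The IDS-C route to entry does not require MDD, and nothing shows that the list was built on any-time or current MDD. An arm difference of 4 or more pre-injury cases has a probability of 14–26% if strata use any-time MDD (assumed prevalence 70–100%, with 20–40% pre-injury), or 30–33% if the stratifier is near-constant and 12–16 of 40 have pre-injury MDD. Those figures apply only under a coding that no section describes. With strata on pre-injury MDD the probability is about 0.3%.

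**Conclusion.** The point holds as a gap in prespecification: the trial stratifies on two factors, and neither document commits them to the efficacy model. If the factors explain 10%, 20% or 30% of the variance in IDS-C change, the unadjusted model overstates the SE by about 6%, 11% or 16%, with the type I error and power losses shown in the table. At 5% or less there is nothing material to gain or lose. These sizes depend on the assumed R², prevalences, block size, alpha and effect. The direction does not: where the factors predict change, the error is a loss of precision, not bias. The wording of the MDD stratum is a matter for clarification only.

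**What to change.** In protocol section VI (Hypothesis 3a) and the SAP (Hypothesis 2a), replace the open covariate sentence with a statement that the efficacy model includes pre-injury MDD and gender, each with its interaction with time, and that any other covariate is used in sensitivity analyses only. With complete data this is equivalent to entering the two factors as covariates in a model of week-12 change. The mixed-model form keeps the plan's intention of analysing all participants when week-12 scores are missing. Adding main effects without the time interactions would not be enough. The statement should be in place before outcomes are compared by arm.

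The cost is two degrees of freedom for the change comparison (40 − 2 = 38 becomes 40 − 4 = 36). If the factors turn out to explain nothing, the simulated SE moves only from 0.314 to 0.315. No new data are needed, because both factors must be known at randomization.

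As a minor clarification, protocol section IV should name the stratum as pre-injury MDD (yes/no), to match the reason and goal in the same sentence.

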For both phases of recruitment, the same study procedures will be used (unless procedures are modified in Phase 3, which will then be submitted for IRB review). The proposed study involves the following points of contact: (1) Obtaining informed consent and screening (may be broken up into multiple visits), (2) biweekly clinician assessments of depressive and neuropsychiatric symptoms (weeks 2, 4, 6, 8, 10), (3) weekly self-report assessments of depressive symptoms for those receiving the intervention, (4) 12 weekly individual CBT-TBI sessions for those randomized to the intervention, (5) a comprehensive assessment at week 12 (primary endpoint), which includes the neuropsychological battery, and (6) a 3-month follow-up assessment for those who received the intervention (randomized pilot only, phase 4). Assessment visits during the 12 weeks of treatment may be completed by phone. The week 12 visit can be split into two parts, with the neuropsychological assessment occurring during the second part, in order to accommodate subjects' potential limitations due to fatigue.

In the context of the COVID-19 pandemic, all in-person procedures will shift to virtual administration via Zoom videoconferencing and/or telephone. When clinical research is safe to resume in-person, select procedures may occur in office when they are unable to occur remotely. For example, participants who do not have access to a computer may go to the Depression Clinical and Research Program to complete computer-based neuropsychological testing (CNS Vital Signs) on a clinic computer. Parking will be reimbursed per standard Depression Clinical and Research Program protocol if participants park in a designated MGH garage.

The following list includes descriptions of each measure being used in the proposed study.

Screening Measures:

UCSD Brief Assessment of Capacity to Consent (UBACC)⁷⁵: 10 item scale assessing capacity for consent.

Demographics Questionnaire: includes age, sex, gender, ethnicity, education, and employment.

*Mini-International Neuropsychiatric Interview (MINI)*⁷⁶: A brief structured diagnostic interview permitting rapid diagnosis of major psychiatric disorders.

Ohio State University TBI Identification Method – Interview Form¹³⁴: A brief interview form for obtaining TBI history and severity.

SCID Psychiatric History: A brief, semi-structured interview form for obtaining basic psychiatric history.

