b. **Range of Safety Reporting to the DSMB** – It is considered necessary for the purpose of monitoring the safety of the study that the DSMB review not only adverse events (AEs) and serious adverse events (SAEs), but other data that may reflect differences in safety between treatment groups. This includes treatment retention rates and reasons for drop-out.

c. Serious Adverse Events – Expedited review will occur for all events meeting the FDA definition of SAEs –

i.e., any fatal event, immediately life-threatening event, permanently or substantially disabling event, event requiring or prolonging inpatient hospitalization, or any congenital anomaly. This also includes any event that a study investigator or the DSMB judges to impose a significant hazard, contraindication, side effect, or precaution. For purposes of this study, all SAEs will be required to be reported to the DSMB, regardless of any judgment of their relatedness to the study intervention. All relevant information will be reported to the DSMB for each SAE including information about the event and its outcome, concomitant medications, the subject's medical history and current conditions, and all relevant laboratory data. Notification by e-mail, and FAX transmittal of all related study forms shall be made to the DSMB within 2 days of the occurrence of any SAE. Information will be reviewed and a determination made of whether there was any possible relevance to the study intervention. Additional reporting to local IRBs will be done

within 24 hours of the SAE. Reporting to the NIH will be made according to their respective regulations governing SAE reporting.

d. **Non-Serious Adverse Events** – At periodic intervals (quarterly during the course of the study and then again at its completion), the DSMB will be provided with un-blinded summaries of the numbers and rates of adverse events by treatment group. These reports will include types of events, severity, and treatment phase.

Data on individual non-serious adverse events is not expected to be needed for this review. e. **Other Safety-Related Reports** – At twelve-month intervals throughout the course of the study, the DSMB will also receive unblinded summary reports of treatment retention and reasons for drop-out, by treatment arm and study phase.

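### At week 12 the C-SSRS is scheduled for the CBT arm only and the AUDIT-C for the waitlist arm only, with no explanation, so the arms cannot be compared on C-SSRS when the controlled period ends

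*Protocol*

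**What the plan says.** Protocol section V sets out the visits in two tables. Table 1, "Schedule of Assessments for Active CBT Patients", marks the C-SSRS at screening, week 12/last visit and the 3-month follow-up, and the AUDIT-C at screening only. Table 2 carries the heading "Schedule of Assessments for Waitlist Patients (note: after WL week 12 patients continue with Active CBT Assessments for 12 weeks"). It marks the C-SSRS at screening only, and the AUDIT-C at screening and at waitlist week 12/last visit.

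The list of points of contact in the same section includes "a comprehensive assessment at week 12 (primary endpoint), which includes the neuropsychological battery". It restricts the weekly self-reports, the CBT sessions and the 3-month follow-up to people receiving the intervention, but puts no such restriction on the week-12 assessment.

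The measure descriptions place the AUDIT-C under Screening Measures ("A 3-item, clinician-rated measure of alcohol consumption") and the C-SSRS under Depression Measures ("Clinician assessment of recent through lifetime suicidal ideation and behavior"). Section IV states that for the first 12 weeks "participants randomly assigned to the waitlist control group will be seen only for assessments".

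**The concern.** Two neighbouring rows show mirror-image marks. For the waitlist arm a screening measure is repeated at week 12 and a suicidality measure is dropped; for the CBT arm it is the other way round. That looks more like a mark entered on the wrong line than a decision, but a site following the tables will collect what they show.

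Waitlist participants attend for assessments only, so Table 2 decides what is recorded on them. As it stands, suicidal ideation or behavior elicited by the C-SSRS after screening can be recorded in the CBT arm alone during the controlled period. Suicidality is not incidental in this population. The protocol's own secondary analysis of TBI Model Systems data reports suicidal ideation in 31.2% and attempts in 3.5% of depressed patients one year after injury. Those are not expected rates for this trial, which excludes acute suicidality. Section IX also asks the DSMB to look at "other data that may reflect differences in safety between treatment groups", and a scale collected in one arm cannot contribute to that.

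**Working it through.** There is no stated figure to reproduce. The check is a row-by-row comparison of the two tables, followed by simple arithmetic.

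**1. The two rows**

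| Measure | Table 1 (CBT) | Table 2 (waitlist) |
|---|---|---|
| C-SSRS | screen, week 12, 3 months | screen |
| AUDIT-C | screen | screen, week 12 |

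**2. Is the reading of the marks sound?** The marks were read from text extracted from the PDF, so alignment matters. Both rows keep their full set of visit cells (14 in Table 1, 7 in Table 2). The rows around them agree between the tables: MINI and the Substance Use Questionnaire are marked at screening only, and CTAS and IDS-C at screening and week 12 (with 3 months added in Table 1). A shift confined to one mark is unlikely but not excluded.

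**3. How unusual is the disagreement?** Thirty-five assessment rows appear in both tables. At week 12:

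- marked in both: 23
- marked in neither: 10 (eight screening rows from consent to MINI, the Substance Use Questionnaire, and QIDS-C)
- marked in one only: 2 (C-SSRS and AUDIT-C)

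23 + 10 + 2 = 35. The rows found only in Table 1 (activity tracker, WAI-SF, STTS-R, post-treatment assessment, homework compliance, end-of-treatment feedback) all concern receiving therapy, which explains their absence from Table 2. The C-SSRS has no such link.

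**4. Participants affected.** The plan randomizes 40. Equal arms are assumed from the balance wording in section IV: 40 / 2 = 20 per arm. Section VI expects retention above 80%: 0.80 × 20 = 16. So about 16 to 20 CBT participants would have a week-12 C-SSRS, against 0 of 20 on the waitlist.

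**5. The next C-SSRS for a waitlist participant.** Treatment is only offered after waitlist week 12. Someone who declines has no marked C-SSRS after screening. Someone who accepts moves to the Table 1 schedule, where the next mark after screening is CBT week 12: 12 + 12 = 24 weeks. This counts from the start of the waitlist period, assumes CBT begins straight after it, and assumes that the Table 1 screening column is not repeated at crossover; the documents settle none of these. Either way, that C-SSRS falls outside the controlled period.

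**The case against.** The strongest reply is that the two schedules were never meant to match. At week 6, eight shared rows (RPQ, Anger-Affect, Neuro-QOL Ability to Participate, Coping Attitudes, Meaning and Purpose, ATQ-R and the two PROMIS Pain scales) are marked for CBT only, also without explanation. The week-12 visit is budgeted at 180 minutes for CBT and 120 for waitlist. The description of the week-12 assessment names only the neuropsychological battery. This shows that arm-specific schedules exist, but it does not account for this pair: a wish to shorten the waitlist visit would not add the AUDIT-C to it.

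A second reply is that nothing planned is lost. This largely stands. Neither protocol section VI nor the SAP analyses the C-SSRS or AUDIT-C. The by-arm DSMB items that section IX names are adverse events, serious adverse events, retention and reasons for drop-out; the C-SSRS is not among them, so its relevance there is an inference from the general wording. Adverse events, QIDS-C and PROMIS Depression are collected every two weeks from week 2 to week 10 in both arms. Adverse events, PROMIS Depression, IDS-C, BDI-II, HADS and the hopelessness scale are collected at week 12 in both. These limit the consequence. They do not replace the C-SSRS, the only listed measure described as a clinician assessment of suicidal ideation and behavior.

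A third reply is that the mark may have been displaced in extraction. There is visible noise elsewhere: the consent/UBACC row of Table 1 is split, and the visit-time row of Table 2 appears to contain a merged cell. Neither is a shift between rows at the C-SSRS and AUDIT-C lines, but the point is fair, and the original page should be looked at first.

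**Conclusion.** The concern holds. Tables 1 and 2 disagree at week 12 on 2 of 35 shared rows, nothing in the text explains it, and as written there is no waitlist C-SSRS to set against the CBT arm at the end of the controlled period. The same is true in reverse for the AUDIT-C. A misplaced mark is plausible but not established.

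The effect is confined to safety description. The IDS-C comparison, and the stated purpose of estimating an effect size, are untouched. The schedule should still be corrected, because it determines what is collected and what can be concluded about suicidality. The row counts rest on the extracted tables; the participant counts also rest on equal arms and the expected retention.

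**What to change.** Check the two rows in the original PDF. If the marks are as described, reconcile Tables 1 and 2 so that the C-SSRS is taken at the same times in both arms over the 12-week controlled period, and state whether the week-12 AUDIT-C is intended for both arms or for neither. If an arm difference is deliberate, give the reason. It would also help to say whether the Table 1 screening assessments are repeated when a waitlist participant starts CBT.

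The cost is a correction to the schedule table and at most one clinician-rated scale at a visit the participant already attends. If waitlist visits have been completed without the C-SSRS, one sentence in the report is enough: C-SSRS change in the CBT arm is uncontrolled, and no between-arm safety comparison is drawn from it.
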